| 5:45 | Breath alcohol (BrAC) reading, use app, self-report of perceived impairment & other measures, then BrAC |
| 6:15 | 1-hour free-drinking period when participants can self-administer more vodka mixed drinks to max BAC=.12% |
| 7:15 | Participant drinks small glass of water to rinse alcohol from mouth, then BrAC |
| 7:45 | BrAC, use app, all participants will get feedback on performance, self-reported impairment/other measures |
| 8pm | Food provided, participants' phones returned and staff extracts data from study phones. |
| 10pm | Usability ratings of assigned app, 4-week field period explained, experimental feedback app provided to all |
| 11pm | Earliest possible dismissal once BrAC \leq .02% |

App condition: The control version is a smartphone-compatible CGNG. Each trial has this order: fixation cross (250ms); blank (250ms), vertical or horizontal cue (white rectangle) for 1 of 6 stimulus onset asynchronies (100, 200, 300, 400, 500, 750ms); go or no-go target (green or blue rectangle, respectively) until participant responds or 500ms; inter-trial interval (250ms). Participants are told to respond fast to green, not to blue. Cues signal a target at 70% probability (horizontal: go, vertical: no-go). Activation and inhibitory tendencies develop cue-dependence^{70, 71}. Go cues speed RT to go targets, which must be overcome for no-go targets.

Inhibition errors are more common after go cues. The app is the same as a computer version except it fits a smartphone (Fig. 2b) with instructions to press the screen directly rather than a keyboard and includes 75, not 250 trials.

The standard version is the same as the control version with the exception that information about performance (correct or incorrect) is displayed along with RT in ms for a correct response during each inter-trial interval.

[figure not shown]

Figure 3. *Example* partial Decision Tree for CGNG Experimental Feedback App use

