The experimental, feedback version includes the standard plus feedback on RT and inhibition errors compared to pre-drinking (Fig. 3). Based on past findings⁴⁵⁻⁵¹, if they react >20 ms slower and/or make $>5\%$ errors, they will get a message summarizing the performance decrement and implications for an outcome, picked randomly among trouble driving, risky sex, drug use, delinquency, or aggression. The app will state that there are simple alternatives with invitation to press a box to view advice, based on research that risk information may increase risky behavior if convenient options are not given⁷². Feedback will be worded non-judgmentally per motivational interviewing tenets.

Post-session field use:

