coefficients in calculating indirect effects of IV on DV, operating through a mediator. When the CI does not include 0, an indirect effect is significant at the specified alpha level.

For Exploratory Aim 1, we will test between-subjects study condition during the lab sessions, amount of alcohol self-administered (operationalized as estimated peak BAC and number of drinks self-administered in separate models) in the alcohol drinking session and during the field period in the intervention and non-intervention periods as predictors of self-reported alcohol consumption (e.g., drinks per drinking day) and alcohol-related problems self-reported at 6- and 12-months post-session on the web-based surveys using MLM. Baseline reports of each alcohol-related outcome and participant sex will be entered as covariates. The web-based surveys at baseline, 6- and 12-months post also include measures of several potential covariates that may be entered into these models should they differ significantly across study conditions.

For Exploratory Aim 2, we will use separate MLMs to test BACTrack Skyn readings during each alcohol administration session as predictors of successive breath alcohol readings taken following alcohol administration/self-administration periods in the alcohol drinking sessions and to predict number of drinks self-administered during the group drinking session. Sex and participant weight will be entered into these models as covariates as well.

For Exploratory Aim 3, we will use MLM to predict expected involvement scores on the CARE measure post-alcohol administration based on performance on the app-based cued go/no-go task following the .06% fixed dose as the predictor variable. Baseline expected involvement scores and scores on the other CARE subscales will be held constant in these models. Since the .06% dose will be administered at each session along with cued go/no-go task performance and the CARE, these measures will be entered into the same models as repeated measures. Participant sex and study condition will also be entered as covariates in these models

Sample, power & effect size

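### Exploratory Aim 3 fits one common performance slope, although in the experimental arm alone poor performance triggers a risk-behaviour message that may affect the ratings

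*Combined protocol and SAP*

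**What the plan says.** In the combined protocol and SAP, Data analyses, the Exploratory Aim 3 paragraph states that "we will use MLM to predict expected involvement scores on the CARE measure post-alcohol administration". The one predictor of interest is how well the participant does on the app's task once the fixed dose has been given. Data from the two sessions are pooled: "these measures will be entered into the same models as repeated measures". Condition enters as follows: "Participant sex and study condition will also be entered as covariates in these models". No condition-by-performance term is listed for this aim. Such interactions are planned earlier in the same section, but only for alcohol self-administration.

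Under App condition, the experimental version compares post-drinking with pre-drinking performance. The trigger is slowing by more than 20 ms, an error rate above 5%, or both. Users who meet it "get a message summarizing the performance decrement and implications for an outcome, picked randomly among trouble driving, risky sex, drug use, delinquency, or aggression". Advice is offered afterwards. The control app shows no performance information. The standard app shows correctness and reaction time trial by trial, but sends no message.

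On order, Table 1 (individual session) and Table 2 (group session) both list, after the dose, "use app, self-report of perceived impairment & other measures, then BrAC". Neither table names CARE. The running text for the individual session puts 30 minutes between app use and the self-reports.

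**The concern.** The aim is about a relation: does worse inhibition under alcohol go with greater expected risk-taking? In the control arm, performance can relate to the rating only through whatever the task measures. In the experimental arm it has a second route, because crossing the performance threshold produces a message about risky behaviour. A condition main effect removes a difference in mean ratings between arms. It cannot remove a difference in slope, because the message depends on the predictor itself. Baseline CARE covariates cannot remove it either, since the message comes after baseline.

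The content overlaps too. In Preliminary Study PS3, task failures were correlated with self-reported aggression, drug use, delinquency and risky sex. Those are four of the five message topics, and PS3 says these relations will shape the app's feedback. The plan itself expects task feedback to change self-appraisal (PS5, Secondary Aim). At stake is the interpretation of one exploratory slope: a weak, or even negative, value could partly reflect the feedback rather than the task.

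**Working it through.** The documents give no effect size, power or sample size for this aim, so there is no stated figure to reproduce. The check asks how far a common slope could move under stated assumptions.

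**Inputs from the documents.** 33 per condition, 99 in total (Sample, power & effect size), taken as all having lab data. Pilot correlations of .47 overall and .31 for the weakest domains (PS3, N=21), used as two possible true slopes.

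**Assumptions, not in the documents.** Poor performance X is a single standardised normal score; the message is sent when X exceeds a threshold c; it is triggered in 25-75% of experimental users; it lowers ratings by m = 0.2 to 0.8 SD; one record per person; equal spread of X in each arm.

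**Formula.** With true slope b, the experimental-arm slope is b - m·φ(c), where φ is the standard normal density. φ(c) is .318 at a trigger rate of 25% or 75%, and .399 at 50%. With equal arms and condition main effects, the common slope is b - m·φ(c)/3.

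- Smallest shift: 0.2 × .318 = .064 in the experimental arm; .064/3 = .021 in the common slope.
- Largest shift: 0.8 × .399 = .319 in the experimental arm; .319/3 = .106 in the common slope.

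| True slope | Experimental arm | Common slope (formula) | Common slope (simulated) | Too low by (simulated) |
|---|---|---|---|---|
| .47 | .406 to .151 | .449 to .364 | .450 to .363 | 4% to 23% |
| .31 | .246 to -.009 | .289 to .204 | .290 to .202 | 7% to 35% |
| 0 | -.064 to -.319 | -.021 to -.106 | about -.02 to -.107 | not applicable |

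The simulation used 600,000 records for each combination of slope, trigger rate and message effect. If the message raised ratings, every shift would change sign.

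**Test behaviour** (4,000 simulated trials, 33 per arm, 50% trigger rate, two-sided .05).

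- No true slope: the common-slope test rejects in about 10% of trials at m = 0.5 and 17% at m = 0.8. The standard and control arms alone give 4.6-5.6%.
- True slope .31: power of the common slope is .68 (m = 0.5) and .51 (m = 0.8), against about .71 in the two arms without the message.
- True slope .47: .99 and .97, against .98.
- Condition-by-performance test: power only about .15 to .37.

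**Cost in precision.** Standard error factors are √(99/66) = 1.22 for the two arms combined and √(99/33) = 1.73 for the control arm alone.

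**The case against.** Several points on the other side stand.

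- **Timing.** A reader might infer that the message comes immediately before CARE, in both sessions. The documents do not establish this. The tables refer only to other measures, the individual-session text has a 30-minute gap, and the Risk Taking Behavior entry under Assessments places expected involvement in the individual session only. What is documented is the order: app use, then self-reports.
- **Overlap.** The PS3 self-report is not called CARE, the CARE domains are not listed, driving is not among the PS3 domains, and each message names one topic at random. Any topic-specific effect on a total score would be diluted.
- **Size.** It is tempting to suppose that feedback flattens or reverses the experimental slope. From .47, flattening to 0 gives a common slope of (2 × .47 + 0)/3 = .313, and reversal to -.30 gives (2 × .47 - .30)/3 = .213. Under the model above these need message effects of at least .47/.399 = 1.18 SD and .77/.399 = 1.93 SD, which nothing in the documents supports for these ratings. The .47 is itself an unadjusted correlation from 21 people (95% CI about .05 to .75).
- **Estimand.** The aim is framed as prediction, so a condition-adjusted average slope is a legitimate, if limited, quantity. All participants use the experimental app in the field period, so performance under feedback is also relevant.

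All arms also hear a general statement linking poor performance to risk. It does not depend on performance, so it neither causes nor cures the slope difference. None of these points shows that the slope is the same in every arm, which is what the planned model assumes.

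**Conclusion.** The point holds as a limitation of the model. One slope is fitted across arms, although performance can act on the ratings through a message in one arm only. On the stated assumptions the common slope would be about 4-23% too low at a true slope of .47 and 7-35% too low at .31. The direction is unknown, and there is no bias if the message does not affect the ratings.

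A reader might go further and conclude that the aim will fail, or that a weak slope would undermine the app's rationale. The documents do not support that: the messages rest on earlier evidence cited in the Background and Preliminary Studies, not on this aim. The aim is exploratory, the study was powered for the primary and secondary aims, and those analyses are unaffected.

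**What to change.** 1. Add condition-by-performance terms to the Exploratory Aim 3 model. Report the slope in each arm with a confidence interval whether or not the interaction is significant; with power of about .15-.37, a null test would not show equal slopes.
2. Prespecify the slope from the standard and control arms combined (n=66) as the estimate free of the feedback message. Give the control-only slope (n=33) as a sensitivity analysis, because the standard app displays trial-by-trial errors. Putting the control-only slope first would be a debatable trade: its power at .31 is about .42, against about .71 for the combined slope.
3. Report the experimental-arm slope separately, as performance under feedback.
4. State where CARE falls relative to app use. Reconcile the Risk Taking Behavior entry (expected involvement in the individual session only; past frequency only at screening) with the Exploratory Aim 3 paragraph (CARE at each session; baseline expected involvement and other CARE subscales as covariates). If there is only one session, the repeated-measures structure falls away.

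The cost is SAP wording. The slope analyses need no new data and follow the approach already planned for self-administration. The combined-arm standard error is about 1.22 times that of the common slope, and the control-only one about 1.73 times.

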 In a pilot study ($N=76$, 67% female, 25% non-white, M age= 43[$SD=14$]), consultant [name] compared a standard CGNG with the app version in his current study, which required 3 min., on average. This app version of the CGNG will be elaborated in the proposed study. Reaction times (RTs) in the app and computer versions were highly correlated ($r=.69$, $p<.01$). The trials in the app version were divided into thirds

[figure not shown]

Figure 2b

and mean RTs were correlated to evaluate reliability. RTs among each third were correlated between .89-.95, indicating strong reliability. Correlations of inhibition errors on the computer version and errors on the app were lower, $r=.28$ ($p=.015$). This is not surprising as CGNG errors are infrequent when sober. This is actually an advantage as it enhances sensitivity to alcohol effects. Given the promising findings and extensive literature on the CGNG⁴⁵⁻⁵¹, we are confident the app version will be sensitive to alcohol. [name] included a description of the app in a preliminary study of young adult drinkers ($N=23$). Participants rated the likelihood they would use the app 5.1 ($SD=1.3$) on a 1-7 scale. In a recent web survey of young adults in FL ($N=72$), [name] found 66% of heavy drinkers reported scores ≥ 3 on a 0-10 scale, indicating agreement they would like to use an app to help reduce drinking, suggesting high interest and a degree of motivation.

Summary: These studies show feasibility; young adults' motivation to use moderate drinking apps even if they take several minutes; our experience with relevant methods; external validity of the CGNG; and reliability and validity of the app version of the CGNG. Thus, the CGNG is a good choice for in-the-moment intervention.

5. Specific Aims

Primary Aim 1: Compare effects of a smartphone app providing feedback on impaired inhibitory control to 2 control conditions on BAC (Aim 1a) and number of alcoholic drinks self-administered (1b) during a 1-hour free drinking period in a naturalistic bar lab that occurs immediately after a fixed alcohol dose targeting BAC= .06%.

Primary Aim 2: In a 4-week period post-session, compare, within-subject, number of drinks per occasion during 2 weeks when participants use the app during actual drinking situations vs. 2 weeks when they will not use the app. Also test app satisfaction including number of times used and likelihood of future use.

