Participants will be otherwise healthy men and women between the ages of 21-25 who frequently engage in heavy alcohol use. This study will test an app based on the cued go/no-go (CGNG) task giving in-the-moment feedback on impaired inhibitory control as an adjunct to an existing, web-based intervention (US-THRIVE) targeting general drinking patterns using M.I. principles. This new app will give in-the-moment feedback comparing pre- and post-drinking RT and errors, referring to evidence that poor CGNG response relates to poor simulated driving and willingness to engage in risky behavior. After feedback, the app will offer advice on slowing drinking and other options to avoid harm (e.g., a taxi). The experimental app—derived from a larger app (Robert Wood Johnson Foundation grant #73293, PIs: [name]/[name])—will be compared to standard (trial-by-trial RT and error information only) and control versions (no information) without feedback. After US-THRIVE, heavy drinking young adults will be randomized to 1 of the 3 apps. After initial use of their randomized app, they will then be dosed to .06% BAC during an individual session in a naturalistic lab, followed by app use. After this initial session, on a separate day, participants will attend a group session including 2 other participants. During this group session; they will again be dosed to .06% BAC, followed by app use, then 1-hr when they can self-administer alcohol up to .12%. There will be at least one day between the individual and group sessions and the goal will be for the individual and group session to occur within 7 days of each other. For 4 weeks post-session, all participants will use the experimental app for 2 weeks in real drinking occasions and not use it the other 2 weeks. Participants completing both the laboratory alcohol administration and field testing components of the study can earn up to \$450 during the course of study participation. Participants may also be invited to complete only field use of the app due to the COVID-19 pandemic or because they cannot physically come to the study location on campus. Among these participants, some will be invited to complete the four-week field use period as described above (i.e., 4 weeks total, 2 weeks with app access, 2 weeks with not and a brief daily questionnaire each day for the 4 weeks). Maximum possible payment for those chosen to complete only the field use period will be \$310. A small subset (up to n= 12 participants) will be selected to complete an ecological momentary assessment based field period of 10 days in which participants will be prompted multiple times per day to either use the app or to complete a brief questionnaire. Maximum payment for those completing the ecological momentary assessment will be \$200. We anticipate enrolling 208 participants, of whom 109 will be eligible with a target of 99 individuals completing the study.

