Our goal was to power the study for the Primary and Secondary Aims. Roberts and Fillmore's findings speak to the potential impact of task-based feedback (Preliminary Study 5 [PS5]). Perceived ability to drive post-alcohol declined from $M=46.8(4.7)$ to $29.7(5.5)$ in the higher risk DUI group and only $M=25.8(5.5)$ to $21.2(4.8)$ in the no-DUI group: a large effect difference ($d=1.5$). While not the same as a control condition, the no-DUIs were a subgroup in which the intervention had minimal impact, as with a control condition. Our alcohol study in-progress (Preliminary Study 1 [PS1]) is relevant as a test of effects of an app on alcohol self-administration though the methods are not identical. Since our ongoing study does not begin with a fixed dose targeting a specific BAC, results involving number of alcoholic drinks self-administered are more comparable to the proposed study and more appropriate for power and effect size estimation. In our in-progress study, the smartphone breathalyzer device/app was associated with significantly less alcohol self-administration ($M=3.5$ drinks, $SD=1.3$) than a control condition ($M=4.8$, $SD=1.5$), $d=.89$. Considering these findings, we project a large effect size.

Aim 1 power is based on ability to detect a between-subjects effect of app condition. We used an effect size equivalent to our in-process smartphone breathalyzer study for effect of condition (experimental vs. control groups). This estimated effect is much smaller than in Roberts and Fillmore's prior study providing feedback regarding cognitive impairment to a sample of drinkers with and without a prior DUI. Assuming an effect ($d=.89$) at $\alpha=.025$ (to account for comparisons between the experimental app and each of the other study conditions: standard and control), the proposed sample of 99 completing the lab session and follow-up period yields .90 power. For Primary Aim 2, the goal will be to compare alcohol use in the 2 weeks participants use vs. do

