not use the experimental app. No study condition effect is hypothesized, thus the focus will be on within-subjects comparison. As such, assuming $\alpha=.05$ at 90% power, we can detect an effect of .33 (small-to-medium). The secondary aim of testing the indirect effect of app condition on drinking via perceived impairment will require the largest sample size as it entails tests of between group differences and tests of indirect effects are underpowered relative to tests of direct effects. In a Monte Carlo simulation, assuming small-to-medium correlation (.35) between perceived impairment and drinks self-administered (DV), power to detect an effect of the IV (study condition) on the mediator and an effect of the mediator on the outcome was $>.90$ and power to detect an indirect effect was .80 with 33 per condition (N=99 total).

7. Possible Discomforts and Risks

Potential risks in this study were identified in accordance with the recommended guidelines on ethyl alcohol administration in human experimentation put forth by the National Advisory Council on Alcohol Abuse and Alcoholism (2005) and two reviews on this subject (Dolinsky & Babor, 1997; Wood & Sher, 2000). Steps taken to minimize these risks were also developed in accordance with these documents.

Alcohol consumption: A number of medical conditions could potentially be worsened by acute alcohol administration (e.g., liver disease, cardiac abnormality, pancreatitis, diabetes, neurological problems, and gastrointestinal disorders). As a result, participants with such medical problems as revealed by a medical history taken during the in-person screening will be excluded from the study.

Alcohol self-administration in a research study by individuals who are severely alcohol dependent as evidenced by current withdrawal or a history of withdrawal may pose a risk to their health and safety. Alcohol self-administration in a research study by individuals who are seeking treatment for alcohol use disorder or who have recently engaged in intensive treatment for alcohol dependence may compromise their efforts to reach or to maintain abstinence or moderate levels of alcohol use.

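### Aim 1 has no stated decision rule for its two app contrasts; naming Holm instead of leaving a fixed .025 implied is an optional, cheap gain in power within the same .05 familywise bound

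*Combined protocol and SAP*

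**What the plan says.** The subsection Sample, power & effect size (Research Plan, section 6) assumes d=.89 for Aim 1 and sets α=.025 "to account for comparisons between the experimental app and each of the other study conditions: standard and control". It concludes that "the proposed sample of 99 completing the lab session and follow-up period yields .90 power". The effect comes from the team's smartphone breathalyzer study, in which the device/app was associated with "less alcohol self-administration ($M=3.5$ drinks, $SD=1.3$) than a control condition ($M=4.8$, $SD=1.5$), $d=.89".

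The same subsection gives the arm size in its mediation calculation: "power to detect an indirect effect was .80 with 33 per condition (N=99 total". The Overview plans on losses: "of whom 109 will be eligible with a target of 99 individuals completing the study". The .90 is therefore computed on completers.

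Specific Aims defines two Aim 1 outcomes: the comparison is made "on BAC (Aim 1a) and number of alcoholic drinks self-administered (1b) during a 1-hour free drinking period".

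The Data analyses section gives multiple regression on condition and sex as the main method. It states no rule for judging the two contrasts and mentions no step-down procedure. The .025 appears once, as an input to the power calculation.

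**The concern.** Half of .05 on each of two contrasts is a Bonferroni split. If it is carried into the analysis unchanged, the second contrast is tested more strictly than familywise control at .05 requires. Once one contrast is significant at .025, the other may be tested at .05 and the error over the pair is still bounded by .05.

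The contrast most affected is experimental versus standard. Under App condition, the standard version already shows correct/incorrect and reaction time after each trial, and the experimental version adds the comparison with pre-drinking performance and the message about consequences. That contrast isolates the new component. Its effect may well be smaller than the .89 observed for a device/app against a control condition. At stake is some power on that contrast, and the chance of showing a difference from both comparison apps.

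**Working it through.** **Inputs.** From the documents: d=.89, α=.025 per contrast, 99 completers, 33 per condition. The documents do not state sidedness; two-sided is assumed because it reproduces .90.

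**1. Reproduce the stated power.** For one contrast with n=33 per arm, the noncentrality is d·√(n/2) = .89·√16.5 = 3.615.
- Two-arm error, 64 df: critical t at two-sided .025 is 2.295; power .904.
- Pooled three-arm error, 96 df: critical t is 2.277; power .908.
- One-sided .025 would give .945 (64 df), which does not match.

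The stated .90 is confirmed.

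**2. The two rules.**
- Fixed split: reject a contrast if its p ≤ .025.
- Holm: if the smaller p ≤ .025, reject that contrast, and also reject the other if its p ≤ .05.

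Holm rejects whatever the fixed split rejects. Both rules reject at least one contrast in exactly the same trials, namely when the smaller p ≤ .025. Holm's .05 bound needs no assumption about the correlation that the shared experimental arm creates.

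**3. Compare them.** One million simulated three-arm trials per setting, 33 per arm, unit SD, pooled error with 96 df. The values .60 and .45 are assumptions; the documents give no estimate for the standard contrast.

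| True d: control / standard | Quantity | Fixed .025 | Holm |
|---|---|---|---|
| .89 / .89 | power, each contrast | .908 | .937 |
| .89 / .89 | both succeed | .845 | .904 |
| .89 / .89 | at least one succeeds | .970 | .970 |
| .89 / .60 | power, standard contrast | .566 | .665 |
| .89 / .45 | power, standard contrast | .331 | .436 |
| .89 / 0 | power, control contrast | .908 | .909 |
| .89 / 0 | false positive, standard contrast | .025 | .046 |
| very large / 0 | false positive, standard contrast | .025 | .050 |
| 0 / 0 | any false positive | .046 | .046 |

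Arithmetic check on the first setting, using P(both) = P(first) + P(second) − P(at least one):
- Holm: .937 + .937 − .970 = .904.
- Fixed split: .908 + .908 − .970 = .846, against .845 simulated (rounding).

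**4. Size of the gain.**
- Plan's own effect: .937 − .908 = about 3 points per contrast; .904 − .845 = about 6 points for both.
- Assumed smaller standard effect: .665 − .566 = 9.9 points at d=.60; .436 − .331 = 10.5 points at d=.45.

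**5. What this does not cover.** Aim 1 has two outcomes, so there are four tests. Applied separately to each outcome, either rule bounds the error over all four at 2 × .05 = .10.

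**The case against.** The strongest objection is that no fixed-split rule has been adopted. The .025 is a sample-size input, and someone intending to use Holm could power at .025 too, since that is Holm's first step. This stands: the documented gap is an unstated rule, and the fixed split is only the rule that the power text suggests.

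A reader might infer that .025 is a mistake or that the study is underpowered. The documents do not support that. The split is valid, the .90 reproduces, and N=99 need not change, because the power section says the mediation aim requires the largest sample.

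A reader might also infer that Holm has the same error rate and costs nothing. It has the same .05 bound, but it spends alpha that the fixed split leaves unused. When only the control contrast is real, at d=.89, the false-positive rate on the standard contrast nearly doubles, from .025 to .046. That is the contrast isolating the new feedback, so the change deserves to be stated openly. Simultaneous confidence intervals that match Holm are also less simple; the plan promises none for Aim 1, so nothing planned is lost.

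Nor does Holm help every contrast in every case: the control contrast gains almost nothing if the standard contrast is null, and the chance of at least one success never changes. The gains near 10 points rest on assumed effects; at the plan's own d=.89 the gain is about 3 points on a test already at its target.

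**Conclusion.** The point holds as an optional, inexpensive improvement. Data analyses should name a rule for the two Aim 1 contrasts, and Holm is at least as powerful as the fixed .025 within the same .05 familywise bound. With 33 completers per arm, two-sided tests and d=.89 for both contrasts, power per contrast goes from about .91 to .94, the chance of both succeeding from about .85 to .90, and the chance of at least one stays at .97. If the standard contrast is d=.45 to .60 (an assumption), its power rises from .33 to .44 or from .57 to .67. Against this stand the higher false-positive rate when only the control contrast is real and the less simple intervals. Multiplicity across outcomes 1a and 1b remains open under either rule.

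**What to change.** Add to Data analyses, before outcome data are analysed by condition: within each Aim 1 outcome, the experimental-versus-control and experimental-versus-standard contrasts are tested by Holm at a familywise level of .05, the smaller p-value at .025 and, if significant, the larger at .05.

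In Sample, power & effect size, keep .90 as the single-contrast power at .025 and add the Holm figures: about .94 per contrast and .90 for both at d=.89. Label any figure for a smaller standard-app effect as an assumption. Say explicitly that the procedure controls error within each outcome and not across 1a and 1b.

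The cost is one sentence in the analysis text and a short addition to the power text, with no change in sample size. If simultaneous intervals are later wanted for Aim 1, they will need more care than Bonferroni intervals.
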